4.2.2. Dose-Limiting Toxicities (DLTs)

DLTs will be evaluated from Cycle 1 Day -16 through Cycle 1 Day 28 (the DLT period). DLTs are drug-related AEs defined as follows:

- Grade 4 neutropenia
- \geq Grade 3 neutropenic infection/febrile neutropenia
- Grade 4 thrombocytopenia
- \geq Grade 3 thrombocytopenia with bleeding
- \geq Grade 3 nonhematologic toxicity (additional criteria for nausea, vomiting, diarrhea, or fatigue: lasting > 5 days with maximal medical management)
- Liver function test abnormalities meeting Hy's Law criteria (aspartate aminotransferase [AST] or alanine aminotransferase [ALT] $\geq 3 \times$ upper limit of normal [ULN] and total bilirubin $\geq 2 \times$ ULN).

4.2.3. Vital Signs

Vital signs include weight, temperature, systolic blood pressure (SBP) and diastolic blood pressure (DBP), pulse rate, and respiration rate.

Vital sign potentially clinically significant criteria are defined in the [Table 7](#) below:

Table 7 Vital Sign Potentially Clinically Significant Criteria

Vital Sign Parameter	Criterion value	Change from baseline
SBP	≥ 180 mmHg	Increase ≥ 30 mmHg
	≤ 90 mmHg	Decrease ≥ 20 mmHg
DBP	≥ 105 mmHg	Increase ≥ 20 mmHg
	≤ 50 mmHg	Decrease ≥ 10 mmHg
Pulse	≥ 120 bpm	Increase ≥ 20 bpm
	≤ 50 bpm	Decrease ≥ 20 bpm
Weight	n/a	Change $\geq 15\%$

bpm = beats per minute

4.2.4. Laboratory

Blood and urine samples for determination of clinical chemistry, hematology, and urinalysis will be collected. The laboratory variables in [Table 8](#) will be measured.

G1 Therapeutics, Inc.
 Clinical Study Protocol G1T38-03
 Statistical Analysis Plan

Laboratory toxicities will be assessed using the NCI CTCAE, Version 4.03. Details on CTCAE grading criteria are presented in the Appendix Table A1. Change from baseline and percent change from baseline in laboratory test results to each assessment will also be derived.

Table 8 Clinical Laboratory Tests

Hematology	Chemistry	
Hemoglobin	Albumin	Potassium
Hematocrit	Alkaline phosphatase	Total protein
WBCs with differential	Total bilirubin	ALT
Platelets	Calcium	AST
	Chloride	Lactate dehydrogenase
	Creatinine	Sodium
	Glucose	Blood urea nitrogen/urea
	Phosphorus	Cystatin C ^a
Urinalysis	Pregnancy test	
Specific gravity	Blood or urine tests are acceptable based on the site's standard clinical practice; applicable to women of childbearing potential only.	
pH		
Glucose		
Protein		
Bilirubin		
Ketones		
Leukocytes		
Hemoglobin		
Microscopic examination (including RBC, WBC, and casts will be performed, if necessary)		

ALT = alanine aminotransferase; AST = aspartate aminotransferase; RBC = red blood cell; WBC = white blood cell

^a Postbaseline Cystatin C to be evaluated in the event that serum creatinine is elevated, if it is available as a local test

Collected serum calcium will not be summarized in tables, instead, corrected serum calcium will be derived from calcium and albumin results based on the following formula:

$$\text{Corrected Calcium} = \text{Calcium (mmol/L)} + 0.02 (40 - [\text{Albumin}] (\text{g/L}))$$

Laboratory Values with < or > Inequality Symbols

Some continuous laboratory data include “<” or “>” symbols. Data will be presented in listings with their inequality symbol; however, for tabulation of summary statistics of safety laboratory results, the given numeric value will be used in the summary statistics, ignoring the nonnumeric qualifier.

4.2.5. Electrocardiograms (ECGs)

All patients will have three 12-lead electrocardiograms (ECGs) performed at the visits indicated in Table 9-1 of the protocol.

G1 Therapeutics, Inc.
 Clinical Study Protocol G1T38-03
 Statistical Analysis Plan

Part 1 Triplicate ECG requirements are as follows:

Cycle and Day	Time Points
Screening	Anytime during visit (one set of 3 ECGs)
Cycle 1 Day -16	Predose and at 2 and 6 hours (\pm 15 minutes) after the G1T38 dose
Cycle 1 Day -2	Predose and at 2 and 6 hours (\pm 15 minutes) after the G1T38 dose
Cycle 2 Day 1 and Day 1 of each cycle thereafter	Anytime during visit (one set of 3 ECGs)

Collected QTcB and QTcF will not be summarized in tables, but will instead be derived from the QT and Heart Rate (HR) based on the following formulas:

- (i) Bazett (obtained in milliseconds): $QTcB = QT / (RR^{1/2})$
- (ii) Fridericia (obtained in milliseconds): $QTcF = QT / (RR^{1/3})$

where QT is measured in milliseconds, RR is derived in seconds from HR in beats-per-minute (bpm):

$$RR \text{ (seconds)} = 60 / (\text{HR in beats-per-minute}).$$

If QT and/or HR is missing, then QTcB and QTcF will be left as missing.

ECG potentially clinically significant criteria are listed in [Table 9](#) below:

Table 9 ECG Potentially Clinically Significant Criteria

ECG Parameter	Criterion- Observed Value	Criterion-Change from Baseline
Heart Rate	>120 bpm	n/a
	<50 bpm	n/a
PR Interval	≥ 210 ms	n/a
RR Interval	>1200 ms	n/a
	<500 ms	n/a
QRS Interval	≥ 120 ms	n/a
	≤ 50 ms	n/a
QT Interval	≥ 500 ms	n/a
	≤ 300 ms	n/a
QTcB, QTcF Intervals	≥ 500 ms	increase ≥ 30 and < 60 ms
	≥ 480 and < 500 ms	increase ≥ 60 ms
	≥ 450 and < 480 ms	decrease ≥ 30 ms and < 60 ms
	>300 and < 450 ms	decrease ≥ 60 ms
	≤ 300 ms	

The average value is used for the criteria if multiple assessments are planned at a nominal timepoint

4.2.6. Echocardiogram/MUGA

An echocardiogram/ multigated acquisition (MUGA) scan to assess LVEF (left ventricular ejection fraction) shall be performed at the time points outlined in Table 9-1 of the protocol.

4.2.7. Treatment Exposure and Compliance

Prescribed duration of treatment (days) is defined as the total number of days that the patient will have been prescribed study medication, that is, including days on treatment before Cycle 1 Day 1 and days on treatment from Cycle 1 Day 1 to treatment end day. Prescribed duration of G1T38 (months) is calculated as (last dose date on the dosing log – first date of continuous daily dosing (C1D1) + x + 1)/30.4375, where x is the number of days patient received G1T38 before C1D1. For example, for a patient who took one dose of G1T38 each on C1D-16 and C1D-2 respectively and took last dose on or after the first date of continuous, daily dosing of G1T38 (C1D1), Days on Treatment = Date of last dose – C1D1 date + 3; for patients who did not start continuous daily dosing, total number of days on dosing of G1T38 before C1D1 will be used as prescribed duration. Prescribed duration of Osimertinib (months) is calculated as (last dose date on the dosing log - the first date of daily osimertinib (only) dosing (i.e., C1D-14) + 1)/30.4375.

The exposure to G1T38 (months) is calculated by (prescribed G1T38 duration - days of interruption as captured in dosing log)/30.4375. Days of interruption is defined as (start date of next record – end date of current record – 1).

For subjects with last dose date is missing from dosing log, if end of treatment date is not missing, date of end of treatment will be used as last dose date. Otherwise, the later date between the last visit date during the treatment phase and last contact date will be used, but the date must be prior to the start of survival follow-up.

Compliance of G1T38 is expressed as a percentage of days G1T38 was actually taken during the treatment phase and will be calculated as exposure to G1T38 divided by prescribed G1T38 duration multiplied by 100.

Dose reduction will be flagged when a total daily dose recorded in G1T38 dosing log is less than the previous entry. Patient with dose interval change but total daily dose unchanged (e.g. 300 mg QD vs 150 mg BID) will not be considered as dose reduction.

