8.3.3. Dose Modification

8 3 3 1 G1T38

Dose adjustments of G1T38 for toxicities are to be made according to the organ system showing the greatest degree of drug-related toxicity. Toxicities will be graded using NCI CTCAE, Version 4.03. No more than 2 G1T38 dose level reductions in total are allowed for any patient. Toxicity that requires dose level reduction more than twice will lead to permanent discontinuation of G1T38 dosing for the individual patient.

Since fatigue can be a symptom of cancer progression, dose reduction will only be performed if the fatigue is deemed to be drug related in the opinion of the investigator.

An off-drug period of up to 21 consecutive days is permitted to allow recovery from any toxicity. Off-drug periods of greater than 21 days may be allowed if the investigator believes the potential benefits of continued treatment outweigh the potential risks, but such cases must be discussed with the medical monitor.

Dose Modifications for G1T38-Related Hematologic Toxicity

The G1T38 dose level adjustments in Table 8-1 are based on hematologic adverse reactions, except lymphopenia (unless associated with clinical events, eg, opportunistic infections).

Table 8-1 G1T38 Dose Level Adjustments Based on G1T38-related Hematologic Toxicities

CTCAE Grade of Hematologic Toxicity	G1T38 Dose Adjustment
Grade 3	Continue G1T38 and repeat CBC at next scheduled visit.
≥ Grade 3 neutropenia associated with a documented infection or fever ≥ 38.5°C ≥ Grade 3 thrombocytopenia associated with bleeding	Withhold G1T38 and monitor counts weekly until ANC \geq 1 x 10 ⁹ /L. Resume therapy at the next lower dose. Withhold G1T38 and monitor counts weekly until platelet count \geq 75 x 10 ⁹ /L. Resume therapy at the next lower dose.
Grade 4	Withhold G1T38 and monitor counts weekly until ANC \geq 1 x 10 ⁹ /L and platelet count \geq 75 x 10 ⁹ /L. Resume therapy at the next lower dose.

ANC = absolute neutrophil count; CBC = complete blood count; CTCAE = Common Terminology Criteria for Adverse Events

Granulocyte-colony stimulating factor

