10.5. Pharmacokinetic Assessments

10.5.1. Pharmacokinetic Sampling

Blood samples for measurement of G1T38 and osimertinib concentrations will be collected as described below and outlined in Table 9-1 (Part 1) and Table 9-2 (Part 2). Information on blood sample collection, handling and storage can be found in the Laboratory Manual.

Part 1

Serial PK blood samples for the measurement of G1T38 concentration in plasma will be collected from all patients in Part 1 on Cycle 1 Day -16 and Cycle 1 Day -2 as outlined in Table 10-2. G1T38 must be administered by clinic staff on Cycle 1 Day -16 and Cycle 1 Day -2.

Pharmacokinetic blood samples for the measurement of osimertinib trough concentration and the G1T38 pre-dose concentration in plasma will be collected from all patients in Part 1 on Cycle 1 Day -2. These samples should be taken **prior to** (within 60 minutes) the morning dose of osimertinib and G1T38. The doses of G1T38 and osimertinib should be taken together, but G1T38 may be given up to 60 minutes after the osimertinib dose.

The actual times of blood sample collections should be documented in the eCRF.

Table 10-2 Part 1: Cycle 1 Day -16 and Cycle 1 Day -2 Blood Sampling Scheme

		Time P	oint (h) Rela	ative to G1T.	38 dose on	Cycle 1 Da	ay -16 and	on Cyc	ele 1 Da	ıy -2
Sample	0 (Pre- dose)	1	2	3	4	6	8	24	32	48
Window	-60 minutes		(± 10 minute	es)	(±	= 20 minute	(± 3 hours ^a)			

h = hour

Actual times will be recorded in the eCRF.

a Samples must be a minimum of 5 hours apart.

Part 2

Patients Randomized to G1T38 + Osimertinib

Sparse blood sampling for population PK analysis of G1T38 will be collected during Part 2 for patients randomized to G1T38 + osimertinib. The goal of this sparse sampling is to obtain G1T38 steady-state blood samples from participating patients at the following time points/intervals relative to G1T38 dosing: predose and at 1 to 3, 3 to 6, and 6 to 8 hours postdose. Each participating patient should have a total of 4 blood samples taken, 1 during each time point/interval (see Table 10-2).

On Cycle 1 Day 15, patients shall be instructed to not take their G1T38 dose at home as the dose will be administered in the clinic following collection of the predose blood sample. In addition, on Cycle 1 Day 15, a blood sample shall be obtained at 1 to 3 hours postdose. It is strongly encouraged that the site contact the patient via telephone prior to the Cycle 1 Day 15 visit to remind the patient not to take the morning dose of G1T38.

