5.2.7. Treatment Duration

Study drug exposures will be summarized for the safety population using descriptive statistics.

G1 Therapeutics, Inc.
Clinical Study Protocol G1T38-03
Statistical Analysis Plan

Exposure to G1T38 and Osimertinib will be categorized in intervals (<3 Months, 3 - <6 Months, 6 - <9 Months, 9 - <12 Months, 12 - <15 Months, 15 - <18 Months, 18 - <21 Months, 21 - <24 Months, >=24 Months) and summarized by dose level and overall. Interval in Months is calculated by duration in days/30.4375.

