5.2.8 Treatment Compliance

G1T38 drug compliance will be summarized using descriptive statistics. The compliance summaries will include the prescribed G1T38 duration (in months), the exposure to G1T38 (in months), and the proportion (%) of days G1T38 is taken. The proportion (%) of days G1T38 is taken will also be summarized in categories “<70%”, “≥70% - <80%”, “≥80% - <90%”, “≥90% - <100%”, and “=100%.” The number and percentage of patients with any G1T38 dose reductions will also be summarized.

Study drug compliance summaries will be based on the safety population.

A listing of exposure and compliance data containing the information described in the sections above will be provided.

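### SAP 4.2.7 converts G1T38 exposure from days to months twice, and does not confine interruption days to the period from Cycle 1 Day 1

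*SAP*

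**What the plan says.** SAP 4.2.7 builds G1T38 compliance from three quantities.

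- **Prescribed duration.** The G1T38 definition begins "Prescribed duration of G1T38 (months) is calculated as (last dose date on the dosing log". It then subtracts the C1D1 date, adds x + 1 and divides by 30.4375, "where x is the number of days patient received G1T38 before C1D1". A patient who never starts daily dosing is given the count of earlier dosing days instead.
- **Exposure.** "The exposure to G1T38 (months) is calculated by (prescribed G1T38 duration - days of interruption as captured in dosing log)/30.4375".
- **Interruption.** "Days of interruption is defined as (start date of next record – end date of current record – 1"), applied to successive records.

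Compliance is exposure divided by prescribed duration, times 100. SAP 5.2.8 reports "the prescribed G1T38 duration (in months), the exposure to G1T38 (in months), and the proportion (%) of days G1T38 is taken" and groups the last of these into bands, the top one being exactly 100%. SAP 5.2.7 gives the conversion for its exposure categories: "Interval in Months is calculated by duration in days/30.4375".

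On the schedule, Protocol 8.1 has single G1T38 doses on Day -16 and Day -2 and daily dosing from Day 1, with no Day 0. Protocol 10.5.1 says "G1T38 must be administered by clinic staff on Cycle 1 Day -16", and the same holds for Day -2. Protocol 8.3.3 adds: "An off-drug period of up to 21 consecutive days is permitted to allow recovery from any toxicity".

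**The concern.** There are two separate problems.

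**Units.** The only prescribed-duration formula for G1T38 yields months. The exposure formula takes that quantity, subtracts a number of days and divides by 30.4375 again. The result is neither days nor months.

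**Gaps.** Interruption is defined purely as a gap between records and is not restricted to records on or after C1D1. The prescribed duration, however, counts only the x days actually dosed before C1D1, not the planned drug-free days around them. If the two pharmacokinetic doses sit in the same log, those planned days are subtracted without ever having been added.

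At stake are the G1T38 exposure and compliance summaries in SAP 5.2.7 and 5.2.8. They are descriptive, but tolerability is a primary objective of Part 1, and Protocol 12.3.1 commits to summarising interruptions, compliance and exposure.

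**Working it through.** **Inputs.** c = 30.4375 and x = 2 for a patient who took both single doses (SAP 4.2.7). Dosing days, absence of Day 0: Protocol 8.1. Day 1 window +2 and Day -2 window ±1: Protocol Table 9-1. Off-drug period of 21 days: Protocol 8.3.3. Write D for the days from C1D1 to the last dose inclusive, D_p = D + 2 for prescribed days, and k for interruption days.

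**The SAP's own example.** With x = 2, last dose - C1D1 + x + 1 = last dose - C1D1 + 3. This matches the worked example in SAP 4.2.7, and it confirms that the drug-free days before C1D1 are not in the prescribed total.

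**Units, prescribed duration in months (literal).** Exposure = (D_p/c - k)/c.

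- k = 0: compliance = 1/c = 3.29%, whatever the duration. At D_p = 170, exposure is 5.585/30.4375 = 0.18 months instead of 5.585.
- k = 21, D_p = 170: (5.585 - 21)/30.4375 = -0.51 months, and -0.506/5.585 = -9%. The correct values are 149/30.4375 = 4.90 months and 149/170 = 87.6%.
- The sign changes at D_p = c × k. For k = 21 that is 639 days, below which exposure is negative.

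**Units, prescribed duration in days throughout.** Exposure = (D_p - k)/c is right. Compliance is then months over days: for k = 0 and D_p = 170, 5.585/170 = 3.29% again. No single unit for the term makes both formulas correct.

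**Gaps, units corrected, both single doses assumed to be log records.** Call Day -16 calendar day 0. With no Day 0 in the study, Day -2 is calendar day 14 and Day 1 is calendar day 16. The gaps are (14 - 0 - 1) + (16 - 14 - 1) = 13 + 1 = 14 days. Moving Day -2 within its window leaves the sum unchanged. Day 1 two days late makes it 16. For a patient who misses nothing, compliance = (D + 2 - g)/(D + 2), where g is the gap total:

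| Days of daily dosing | g = 14 | g = 16 |
|---|---|---|
| 28 | 16/30 = 53.3% | 14/30 = 46.7% |
| 56 | 44/58 = 75.9% | 42/58 = 72.4% |
| 84 | 72/86 = 83.7% | 70/86 = 81.4% |
| 168 | 156/170 = 91.8% | 154/170 = 90.6% |
| 336 | 324/338 = 95.9% | 322/338 = 95.3% |

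- Exposure is negative for D below 12 (g = 14) or below 14 (g = 16).
- Reaching 90% needs D ≥ 10g - 2, that is 138 or 158 days.
- A patient with only the two single doses gets 2 - 13 = -11 days (-10 to -12 with the Day -2 window).
- A patient with only the Day -16 dose has no gap and no error.

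**Both errors, read literally, same assumption.** Exposure is negative while D + 2 < 14 × 30.4375 = 426.1, so through D = 424.

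**The case against.** The best reply on units is that the intent is plain. SAP 4.2.7 opens with a general prescribed duration in days, its worked example is a day count without division, compliance is described there as a share of days, and SAP 5.2.7 makes one conversion. A programmer reading all of this would probably arrive at the right calculation. Uniform compliance of 3.3% or negative exposure would also be noticed in the tables or the patient listing, and the 21-day hold is a permitted period whose frequency is unknown. This makes a drafting error likely and wrong published figures unlikely. It does not make the text right: the same term would have to mean days in one formula and months in the next, and the SAP does not say so.

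On gaps, the reply is that neither document shows the dosing log. Administration by clinic staff does not tell us where the doses are recorded. The separate term x shows that the authors had the pharmacokinetic period in mind, and the reference to interruptions captured in the log could mean true interruptions only. The uncertainty about recording stands, so the effect is conditional. However, the next sentence defines interruption as a bare record gap with no C1D1 limit, and that wording does not exclude the planned days.

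It is also true that the consequence is limited. Part 1 has no formal test, and dose reductions are flagged from total daily dose independently of these formulas.

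**Conclusion.** The concern holds. The unit error is certain on the text: as written, the formulas give 3.3% compliance to a patient who never interrupted dosing, and negative exposure to many who did. It is most likely a drafting slip.

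The missing C1D1 limit is also a fact of the text, but its effect depends on both single doses being dosing-log records. If they are, the shortfall is 14 to 16 days per patient who took both doses and started daily dosing. It is largest proportionally for those treated briefly, and none of these patients could reach the 100% band. If they are not, this second part has no effect.

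The damage is confined to the descriptive exposure and compliance summaries. No rule for dose-limiting toxicity, adverse events, efficacy or the recommended Phase 2 dose uses these quantities. It should be fixed because the specification gives wrong results and the correction is simple.

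**What to change.** Rewrite the G1T38 derivations in SAP 4.2.7 in days and convert once:

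- Prescribed days D_p = last dose date - C1D1 date + 1 + x, or x if daily dosing never starts.
- Interruption days: gaps between successive dosing-log records, counting only records on or after C1D1.
- Exposure days = D_p - interruption days.
- Compliance = exposure days / D_p × 100.
- For display in months, divide prescribed days and exposure days by 30.4375, once each.

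Checks for the program: uninterrupted dosing through Day 168 with both single doses should give 170 days, 5.585 months and 100%. The same patient with 7 interruption days should give 163 days, 5.355 months and 95.9%.

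The cost is two or three sentences in SAP 4.2.7 and the matching code. No new data are needed and no other analysis changes.

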5. ANALYSIS METHODS (PART 1)

5.1 General Principles

5.1.1. General Statistical Considerations

All statistical analyses will be performed using SAS® Version 9 or higher.

Data will be summarized descriptively by dose level and overall.

G1 Therapeutics, Inc.
Clinical Study Protocol G1T38-03
Statistical Analysis Plan

The descriptive summary for the categorical variables will include counts and percentages. The descriptive summary for the continuous variables will include mean, median, standard deviation (SD), and minimum and maximum values. The descriptive summary statistics of time to first objective response will include median, 25% and 75% percentiles, and minimum and maximum values. The Kaplan-Meier method will be used to estimate the probability of survival (PFS and DOR) and the respective the time-to-event percentiles.

In general, the precision of descriptive statistics for continues variables min and max will always be consistent with the precision of the variable of summarization. Additional rounding rules are listed as follows:

- If the original value has <= 1 decimal places, mean and median will have one more decimal as the original value. Measures of variability (e.g, SD will be rounded two more decimal places than the precision of the original measure.
- If the original value has two decimal places, mean and median will have the same decimal places as the original value. Measures of variability will be rounded one more decimal place than the precision of the original measure.
- If the original value has >2 decimal places, all the descriptive statistics will have the same decimal places as the original value.

For categorical variables, non-zero percentages will be displayed with 1 decimal place, zero-percentage will not be displayed. A percentage value less than 0.1% will be displayed as “<0.1%.” A percentage value less than 100% but greater than 99% will be displayed as “>99%.”

Part 1 of the study is descriptive in nature. No formal statistical test will be conducted. Two-sided 95% exact CI will be provided for tumor response rate by using Clopper-Pearson method. 95% CI will be provided for PFS percentiles by using log-log transformation approach.

Any rounding will be done after all calculations are made.

Safety assessments (other than AEs) during treatment period is defined as assessment that is evaluated between the date of first dose of study drug and the date of last dose of study drug + 29 days. Assessments occur on or after last dose of study drug + 30 days will be counted as assessments during post-treatment period. If start date of survival follow up is available, assessments during post-treatment period should occur prior to the start of survival. If the last dose date of study drug is missing, any assessment/event occurring after the start of study drug will be considered as during treatment period.

All data will be listed for all enrolled patients.

